3.3 Hypothesis

Our current expectations are that PrC-19 will show differences in swallowing function and physiology compared to age- and sex-matched reference values ([name], 2019), as listed in the following table:

Parameter	Prediction in PrC-19 (vs age-matched healthy reference values)
Penetration-Aspiration	Higher frequency and more likely to be silent
Time-to-Laryngeal-Vestibule-Closure (LVC)	Later closure due to priority of respiration
LVC duration	Shorter due to underlying respiratory challenges
Pharyngeal Area at Rest	Larger due to muscle weakness and atrophy. Note: reference values show significant sex difference with larger area in males.
Pharyngeal Area at Maximum Constriction	Larger (i.e. poor constriction) due to muscle weakness and atrophy
Residue	Greater due to poor constriction
# of swallows per bolus	Higher due to poor bolus clearance

We expect PrC-19 patient to report swallowing-related burden. We hypothesize that post-swallow inspiration (a sign of respiratory-swallow discoordination) will be seen more commonly in PrC-19 compared to healthy reference data (Valenzano et al, 2020), and will be particularly common in those who report dyspnea.

4.0 Study Design

This is an observational study, in which people recovering from COVID-19 infection will attend two outpatient clinic visits for a comprehensive swallowing assessment. The assessment will include a videofluoroscopy, measurement of respiratory-swallow coordination using a digital stethoscope, measures of tongue and cough strength, and patient-reported measures that will help us to understand the presence and impact of swallowing impairment (dysphagia) in this population, as compared to reference data from healthy adults that has previously been collected and published by our lab.

Data Collection Procedure

We expect study participation to involve an initial 30 minute telephone or video conference call to review the consent documents, a 60 minute session to capture non-radiographic data, and a 60 minute session to capture the radiographic data. If requested, it is possible to arrange for both of the data

collection appointments to take place on the same day, although it is not possible to guarantee back-to-back scheduling and a delay between the sessions is likely.

Infection Control and Safety Procedures for the Face to Face Appointments:

- a. We will contact the participant 2 days prior to each study appointment and use the UHN COVID 19 screening questions to confirm that they do not have any current symptoms of COVID-19 that are not otherwise explained and are suggestive of possible active infection. This will also confirm that they have not, to their knowledge, been exposed to someone who has active COVID-19. Two hours prior to each appointment, we will ask them to complete the UHN COVID-19 screening app questions on their smart phone (at www.UHNScreen.ca), or, to arrive at the facility in time to undergo routine COVID-19 screening prior to entering the facility. If the participant is accompanied by a companion, the companion will also need to complete these routine COVID-19 screening procedures. Upon arrival, they will be issued with a procedure mask to wear at the hospital.
 - b. For the initial appointment scheduled in the Swallowing Rehabilitation Research Laboratory at Toronto Rehab, the participant and their companion will be met in the Elm Street waiting room area at Toronto Rehab and escorted by a study team member directly to the 12th floor Swallowing Lab.
 - c. For the x-ray appointment at Toronto General Hospital, the participants will be given instructions on how to enter the hospital at the Elizabeth Street entrance where COVID-19 screening is performed, and how to reach the Diagnostic Imaging department, and will be met there by a member of the study team.
 - d. The study team members present for data collection will follow IPAC rules for limiting potential spread of infection. All study team members who will be directly involved in data collection are licensed speech-language pathologists who will have been required to review the lab's standard operating procedures relating to infection control and safety. They will be required to wear procedure masks at all times and to maintain 2 meter distancing from the participant and the other team members present, whenever possible. Regular disinfection of surfaces in the lab using appropriate wipes will be part of the study protocol. For study staff members who will perform tasks that require close physical proximity to the participant with less than 2 meters distance, additional personal protective equipment (PPE) will be used in accordance with IPAC recommendations, including wearing laundered gowns, gloves, face shields, and, if appropriate, N95 masks. Regular hand washing and sanitizer use will also be required. There will always be a minimum of 2 study team members present, and a buddy system will be employed to observe donning and doffing of PPE and to prompt whenever necessary to ensure adherence to safe PPE practices. These procedures have been reviewed and approved by the KITE Research Restart team.
1. Review of study information and consent form:
 - a. All participants who show an interest in participating will be provided with the study information and consent form ahead of time. These documents will be sent either by

email or by mail, according to the participant's preference for delivery method. A telephone or video-conference call will be scheduled to review these documents and answer any questions.

- b. For participants who wish to proceed, we will obtain an initial verbal consent that they have understood all the information provided, and, after verifying that they have no more questions, we will move forward with scheduling the study appointments. If the participant wishes, the study questionnaire can be mailed to them for review in advance of their first appointment. However, completion of the questionnaire will not take place prior to the first appointment or prior to signing the consent form.
 - c. During the first appointment, we will review the study procedures and answer all their questions. If they wish to proceed, we will ask them to sign the consent form. A copy of the consent form will be provided to the participant. Data collection will proceed only after these steps have been completed.
2. Demographic and medical history information:
- e. Participants will be asked to complete a form capturing demographic, medical history and history of COVID-19 management. Those participants who answer yes to questions inquiring about current respiratory difficulties (shortness of breath) or swallowing difficulties will be asked to complete the section of the questionnaire incorporating the Modified Medical Research Council Dyspnea Scale and the Sydney Swallow Questionnaire to understand these symptoms in more detail. For those who report no current symptoms of respiratory or swallowing difficulty, this section may be left blank.
3. Non-radiographic data:
- a. Bulbar muscle strength will be measured using 3 repetitions of a maximum effort isometric tongue-to-palate press task, measured using the Iowa Oral Performance Instrument. The patient will be instructed to "squeeze the bulb as hard as you can between your tongue and the roof of your mouth". A clean, single-use, disposable tongue bulb will be used for each participant.
 - b. Voluntary peak cough flow will be measured using a Mini-Wright analog peak flow meter fitted with a single-use, disposable expiratory one-way valve filter mouthpiece following the American Thoracic Society (ATS) standards. The patient will be instructed to "cough hard like there is something stuck in your throat" and will perform three trials.
 - c. Respiratory-swallow coordination data will be collected using the E-Steth digital stethoscope during a water swallow screening task. The E-steth stethoscope housing will be sanitized with alcohol wipes prior to and after use. The housing itself will not come into direct contact with the participant's neck, because there will be medical adhesive tape between the participant's skin and the device housing. Nevertheless, we will use a fresh e-steth device for each participant and will dispose of the device after use with each participant. After sanitization, the E-Steth housing will be attached to the participant's neck using double sided tape, over the suprasternal notch. The E-Steth output will be connected to a dedicated lab cell phone/MP3, iPad or laptop computer running the Voice Memos application and recorded as .m4a files. The participant will be

provided with a cup containing 60 ml of chilled bottled water and asked to take a comfortable sip and swallow. This procedure will be repeated up to 4 times. If the patient completes all 4 sips in without any overt signs of aspiration, a new cup containing 90 ml of water will be provided, and the patient will be asked to drink the entire 90ml in a sequential fashion without stopping.

Stopping rule: If the patient demonstrates obvious signs of aspiration, including coughing post-swallow at any point in the water swallow screening task, further water screening will be discontinued.

- d. Following completion of the first appointment, the participant will be given instructions for their second appointment at the Toronto General Hospital diagnostic imaging department for the x-ray component of the study. If requested, it is possible to arrange for both of the data collection appointments to take place on the same day, although it is not possible to guarantee back-to-back scheduling and a delay between the sessions is likely.

4. Radiographic data:

The standardized videofluoroscopic swallowing study will be performed in the Diagnostic Imaging Department at the Toronto General Hospital. Swallowing x-ray appointments are always scheduled during a Tuesday afternoon time-slot. Upon arrival at the Toronto General Hospital entrance, the participant (and any companion) will again need to pass through the routine COVID-19 screening procedures before entering the building.

The x-ray procedure will involve swallowing 3 boluses each of thin, mildly thick and extremely thick barium and 1 consecutive drinking task of thin liquid.

Stimulus preparation: Bracco E-Z-Paque® powdered barium will be prepared in 20% w/v concentration with water, and thickened to target consistency using Resource Thicken-Up™ Clear (a xanthan gum thickener developed by Nestlé Health Science). Target consistency will be defined using the International Dysphagia Diet Standardisation Initiative definitions and Flow Test. For the Toronto site, all stimuli will be prepared in the Swallowing Rehabilitation Research Laboratory not longer than 6 hours prior to scheduled use, according to a strict standard operating procedure. Barium stimuli will be transported to the radiology suite at Toronto General Hospital, as per routine clinical procedures. Similar procedures will be followed at the Hamilton and Florida sites.

Procedure: Three cups of each stimulus will be prepared for the experiment, each containing 40 ml and organized in a muffin tray placed in front of the participant. If the participant completes all 3 thin sips without any observation of aspiration or serious residue, a new cup containing 90 ml of thin liquid will be provided, and the participant will be asked to drink the entire 90ml in a sequential fashion without stopping. This is a routine clinical method for ruling out swallowing safety concerns in patients who do not show concerns on single sip tasks. Single-use plastic teaspoons will be placed in the extremely thick cups to facilitate serving. The participant will be asked to take a

comfortable sip (or spoonful) from each cup. The cups will be weighed on a digital balance at the conclusion of the session to derive estimates of sip volume. The order of testing will begin with thin liquids and proceed to mildly thick and then extremely thick stimuli.

Recording: The videofluoroscopic swallowing study will be captured in lateral projection using pulsed videofluoroscopy at a rate of 30 pulses per second, and recorded on a synchronized videocapture system at 30 frames per second. The recording system is a secure TIMS Dicom system with password access that is connected to the hospital's network, enabling secure saving of all recordings in a folder on our research server. Any identifiers visible on the x-ray image (such as the participant's MRN number or age) will be hidden with black electronic screen scrubbers during the first step of data processing and prior to assignment for review.

Stopping rules: Testing of each consistency will be discontinued after the second observation of aspiration or serious residue. The entire protocol will be terminated after the 4th observation of aspiration. The sequential thin drinking task will only be performed if the participant completes all 3 thin sips without any observation of aspiration or serious residue.

Compensation

Participants will receive a \$50 e-gift card for participating in this study.

File Transfer

All data processing will take place at the KITE Research Institute - Toronto Rehabilitation Institute - University Health Network. Each institution will be required to sign a data transfer agreement prior sending any data. We will use secure file transfer procedures to transfer the necessary data from the collaborating sites to the Toronto lab.

ClinicalTrials.gov Registration

A description of this clinical trial will be available on <http://www.ClinicalTrials.gov>, as required by U.S. Law.

5.0 Selection of Subjects

Participants

We aim to conduct 100 assessments (approx. 25 per collaborating site involved in the study and approx. 50 at University Health Network) over a 14-month period.

Recruitment

We will adopt three strategies for recruiting participants to this study:

1) We have linked to the Ontario COVID-19 Prospective Cohort Study (OnCoP) study being conducted by the CANCOV study PIs Drs. [name] and [name] at UHN. The CANCOV study team has agreed to notify their participants of the opportunity to participate in our study. They will use our

study information sheet and referral form for this purpose. They have also suggested that a Swallowing Team Member could attend their weekly clinic and speak directly to CANCOV participants who agree to consider the study.

2) We will work through the members of our clinician advisory group and a wider network of clinicians in the cities where data collection is happening to solicit referrals of patients who meet the study inclusion criteria. We will ask these clinicians to introduce the study opportunity to patients and request permission to complete a referral to the study team for future contact.

3) We will conduct a broad public advertising campaign through local newspapers, magazines, websites, mailings and posters at community centres, seniors' residences, places of worship, and around the university and hospital campuses of the study sites (University of Toronto, University Health Network Toronto, McMaster University, Hamilton Health Sciences Centre, University of Florida, Shands Medical Centre).

The clinical research coordinator will respond to all inquiries or referrals regarding potential participation, contacting the patient by phone or videoconference using Microsoft Teams to discuss the study further, obtain initial verbal consent and schedule the study appointments. A reminder call will take place 2 days before the scheduled study appointments.

Inclusion Criteria

- Adult (18 years of age or older)
- Positive (or presumed positive) diagnosis of COVID-19 infection not earlier than March 1, 2020
- At least 2 weeks post positive diagnosis and medical management of COVID-19 infection
- Currently free from fever or chills; new onset of cough; worsening of chronic cough; new onset of sore throat; new onset of nausea/vomiting, diarrhea, stomach pain; eye pain or conjunctivitis; unexplained headaches, fatigue, malaise or muscle aches. Individuals with continuing complaints of shortness of breath, difficulty breathing, swallowing difficulty or decrease/loss of sense of taste or smell will be included.
- Adequate comprehension of English (able to understand consent form and follow study instructions)

Exclusion Criteria

We will accept any participants who meet the inclusion criteria, regardless of prior medical history. As indicated under the inclusion criteria, children under the age of 18 years old will not be involved in this protocol due to the use of radiation. Additionally, pregnant women will be excluded due to the use of radiation.

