STUDY PROTOCOL

**The Pathophysiology of Swallowing Impairment in
People recovering from COVID-19 Infection**

NCT 04537650

PI: [name].

Swallowing Rehabilitation Research Laboratory

KITE Research Institute, Toronto Rehabilitation Institute, University Health Network

TABLE OF CONTENTS

LIST OF ABBREVIATIONS	3
PROTOCOL SUMMARY	4
1.0 General Information	6
2.0 Introduction	7
3.0 Study Objectives and Hypothesis.....	7
3. 1 Purpose	7
3.2 Objectives.....	9
3.3 Hypothesis.....	10
4.0 Study Design.....	10
Data Collection Procedure	10
Compensation	14
File Transfer	14
ClinicalTrials.gov Registration	14
5.0 Selection of Subjects	14
Participants	14
Recruitment	14
Inclusion Criteria	15
Exclusion Criteria.....	15
6.0 Risks and Benefits	15
Risks	15
Benefits	16
Incidental Findings	16
7.0 Statistics	16
8.0 Data Safety and Monitoring Plan.....	17
9.0 Data Handling and Record Keeping	17
10.0 Conflicts of interest.....	18
11.0 Additional Ethics Reviews	18
12.0 References	18

LIST OF ABBREVIATIONS

PrC-19	People recovering from COVID-19
VFSS	Videofluoroscopic Swallowing Study
LVC	Laryngeal Vestibule Closure

PROTOCOL SUMMARY

Full Title	The Pathophysiology of Swallowing Impairment in People Recovering from COVID-19 Infection.
Short Title	Swallowing impairment after COVID-19.
Sample Size	N=100 (approximately 25 at each collaborating site and 50 at the University Health Network)
Study Population	Patients who are recovering from COVID-19 infection.
Accrual Period	October 15, 2020 to January 31, 2022
Study Design	This is an observational study, in which people recovering from COVID-19 infection will attend two outpatient clinic visits for a comprehensive swallowing assessment. The assessment will include a videofluoroscopy, measurement of respiratory-swallow coordination using a digital stethoscope, measures of tongue and cough strength and patient reported measures that will help us to understand the presence and impact of swallowing impairment (dysphagia) in this population.
Study Duration	October 15, 2020 to January 31, 2022

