- e) Participants may experience skin irritation due to the adhesive patches and medical tape used to attach the E-steth sensor to the neck. Individuals who report known skin sensitivity or allergies to adhesives will be given the option to decline the E-steth component of the study.

Benefits

Participants will benefit by receiving a comprehensive swallowing assessment that may not otherwise have been available to them.

Incidental Findings

In the unlikely event that the video x-ray reveals an unexpected medical finding, the team will generate a report and will facilitate referral to appropriate follow-up services.

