7.0 Statistics

We will use the ASPEKT Method ([name] et al., 2019) to analyze available recordings of thin liquid, mildly thick liquid and extremely thick liquid swallows, and compare values to age matched reference data ([name] Swallowing Lab, 2019). Our goal is to develop an understanding of the prevalence of

abnormal values in PrC-19 taking comorbidities and other related factors into consideration. These potential covariate moderators include demographic factors (sex, age, gender, race, ethnicity), pre-existing or co-existing medical diagnoses, history of the COVID-19 hospitalization including details of any ventilator support required, medical history since discharge (including any occurrences of respiratory infection), dyspnea, changes in taste and/or smell associated with the COVID-19 infection, bulbar muscle strength, cough strength, and abnormal respiratory-swallow coordination. Additionally, the person's ability to tolerate the full range of diet textures and their swallowing-related quality of life may be affected by COVID-19 related swallowing difficulties.

Assuming 100 participants and 3 boluses per consistency, this will result in a dataset of 300 boluses per consistency. Our previous research suggests that swallowing can differ across repeated boluses of the same consistency within an individual. It is, therefore, reasonable to calculate statistical power at the bolus level. A power calculation in Study Size software suggests that a sample of 138 boluses for a given consistency will be needed to detect frequencies of abnormal values higher than those seen in the healthy reference sample with odds ratios ≥ 2.00 with 80% power. Therefore, the targeted sample size should be sufficient both to detect increased frequencies of abnormal values and to allow the bivariate exploration of the impact of single covariate moderators on abnormal value frequency. We will not have sufficient data to create a multivariate model exploring the relative impact of different moderators; however the findings from this analysis will be sufficient to inform future studies in larger cohorts.

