8.0 Data Safety and Monitoring Plan

A clinician advisory panel comprising 9 speech-language pathologists who work in critical care has been established to guide this study. Additionally, 3 physicians have agreed to provide medical advice to the study team. The clinician advisory group will meet via video-conference every 4-6 weeks over the course of the study. [name], PhD, SLP(C), Reg. CASLPO will act as chair. Progress reports will be provided for review 1 week ahead of these meetings, and presented to the meeting. These reports will document the numbers of participants accrued, preliminary trends in the data and any adverse events. After discussion, the principal investigator, co-investigators, collaborators and study coordinators will leave the call, to allow for further in camera discussion. In the event that any concerns about study continuation are raised during the in camera session, [name] will report these back to the study team.

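### Prevalence is the stated goal, but three opt-in recruitment routes are pooled and neither route nor swallowing complaint is a planned moderator, so the frequency may be inflated by an unknown amount

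*Combined protocol and SAP*

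**What the plan says.** The Protocol Summary labels the study population "Patients who are recovering from COVID-19 infection", with no requirement of a swallowing complaint. Section 7.0 states the aim: "Our goal is to develop an understanding of the prevalence of" abnormal values in that population, with comorbidities and related factors taken into account.

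Section 5.0 (Recruitment) gives three routes:
- Linked cohort: "The CANCOV study team has agreed to notify their participants of the opportunity to participate in our study".
- Clinicians in the advisory group and a wider network, who are asked to "solicit referrals of patients who meet the study inclusion criteria".
- Advertising: "We will conduct a broad public advertising campaign through local newspapers, magazines, websites, mailings and posters".

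None is described as consecutive or random, and no log of people approached or declining is described.

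Three other passages bear on who comes forward. Section 8.0 describes the advisory group: "A clinician advisory panel comprising 9 speech-language pathologists who work in critical care has been established to guide this study". Section 6.0 (Benefits) says: "Participants will benefit by receiving a comprehensive swallowing assessment that may not otherwise have been available to them". The inclusion criteria say: "Individuals with continuing complaints of shortness of breath, difficulty breathing, swallowing difficulty or decrease/loss of sense of taste or smell will be included".

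The potential moderators in Section 7.0 cover demographics, other diagnoses, the COVID-19 hospital course including ventilation, later medical history, dyspnea, taste and smell, tongue and cough strength, and breathing-swallow coordination. Recruitment route, site and current swallowing complaint are not named. Only one-at-a-time exploration is planned. The intake form in Section 4.0 does ask every participant about current swallowing difficulty.

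**The concern.** A prevalence needs a sample whose entry does not depend on the condition being counted. Here every route requires the person to opt in, the benefit on offer is an examination of the very function under study, and part of the referral network consists of speech-language pathologists. It is a reasonable inference, though the documents do not state it, that people who notice trouble swallowing are more likely to be referred or to respond.

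If so, two results are affected. The pooled frequency would overstate how common abnormal values are among recovering people. The comparison with healthy reference values, on which the hypotheses in Section 3.3 rest, would be shifted in the hypothesised direction. Adjusting for hospital course or dyspnea would not remove selection that acts through swallowing complaints, and a route that was never recorded may be hard to recover later.

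**Working it through.** **The plan's own figure.** Section 7.0 gives 138 boluses per consistency for an odds ratio of 2.00 or more with 80% power. It states no reference rate, significance level or sidedness. A two-sample formula at an assumed two-sided 5% gives 283 per group at a 10% reference rate, 172 at 20%, 141 at 30%, 135 at 35% and 137 at 50%; one-sided, it gives 135 at 20%. So 138 is attainable under some assumptions and is not shown to be wrong. This point does not depend on it. The 2.00 serves below only as a yardstick.

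**Inputs for the selection check, all assumed.** The documents give no enrolment data by route or complaint.
- p: true frequency among all recovering people
- k: how many times as likely an affected person is to enrol as an unaffected one, through a selective route
- s: share of the sample coming by such routes

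**Formulas.**
- Frequency within a selective route: p′ = pk / (pk + 1 − p)
- Frequency in the pooled sample: f = s·p′ + (1 − s)·p
- Apparent odds ratio against all recovering people: [f/(1 − f)] / [p/(1 − p)]

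**Worked cases at p = 10%.**
- k = 1.25, s = 0.5: p′ = 0.125/1.025 = 0.122; f = 0.5 × 0.122 + 0.5 × 0.10 = 0.111; odds ratio 1.12.
- k = 2, s = 1: p′ = 0.2/1.1 = 0.182 = f; odds ratio (0.182/0.818)/(0.10/0.90) = 2.00.

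| p | k | s | Sample frequency | Apparent odds ratio |
|---|---|---|---|---|
| 10% | 1.25 | 0.5 | 11.1% | 1.12 |
| 10% | 2 | 0.5 | 14.1% | 1.48 |
| 10% | 3 | 0.5 | 17.5% | 1.91 |
| 10% | 2 | 1 | 18.2% | 2.00 |
| 20% | 1.25 | 0.5 | 21.9% | 1.12 |
| 20% | 2 | 0.5 | 26.7% | 1.45 |
| 20% | 2 | 1 | 33.3% | 2.00 |

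When the whole sample is selective, the apparent odds ratio equals k whatever p is.

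**What these odds ratios compare.** They set the sample against all recovering people. The plan's 2.00 sets patients against the healthy reference. The two are linked by multiplication:

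OR(sample vs healthy) = OR(sample vs all recovering) × OR(all recovering vs healthy)

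An assumed example: 25% of recovering people have complaints, 40% of them are abnormal, and 10% of the others are. The true frequency is 0.25 × 0.40 + 0.75 × 0.10 = 17.5%. If 60% of the sample has complaints, it shows 0.60 × 0.40 + 0.40 × 0.10 = 28%. The selection odds ratio is (0.28/0.72)/(0.175/0.825) = 1.83. With a healthy rate of 10%, the true odds ratio is (0.175/0.825)/(0.10/0.90) = 1.91, and the observed one is 1.83 × 1.91 = 3.50. Selection there exaggerates a real excess; it does not create one. Selection accounts for the whole observed excess only if recovering people and the healthy reference have the same frequency.

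**Limit of the check.** It works at person level, whereas the primary outcomes are bolus frequencies per consistency. It shows scale, not a forecast.

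**The case against.** The strongest reply is that nothing in the documents shows inflation. Clinicians are asked to refer anyone who meets the criteria, and those criteria require no swallowing complaint. The wording of the advertisements is not given. Some features could act the other way: people with worsening chronic cough or unexplained fatigue or malaise are ineligible, and the $50 gift card rewards attendance with or without symptoms. Severity, comorbidity and dyspnea are to be explored, the moderator list is worded as potential rather than closed, and Section 7.0 presents the findings as input to larger studies. Complaint status is already collected, and cohort notification and clinician referral both use referral forms.

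Most of this stands, and it limits the claim. A reader might infer that the frequency is inflated, or that selection alone would deliver the target odds ratio. The documents support neither: they hold no data on who enrols, and the second inference also treats two different comparators as one. A reader might also take the linked-cohort participants as the best prevalence estimate. That route is opt-in too, and the cohort is an Ontario study run at the lead centre, so route is entangled with site. Florida participants would presumably come only by referral or advertising.

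The reply does not remove the gap. The case-mix covariates do not capture self-selection on swallowing symptoms, the plan makes no use of complaint status as a moderator, it does not mention recording route, and it does not qualify the word prevalence.

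**Conclusion.** The point holds as a risk of unknown size. The plan sets prevalence as its goal, pools three opt-in routes into a study whose benefit is a swallowing assessment, and has no means of detecting self-selection. Upward bias is the likelier direction, but that is a judgement from the design, not a finding. On the assumed inputs the apparent odds ratio against all recovering people runs from about 1.1, which is trivial, to 2.0, numerically equal to the design effect though measured against a different comparator. The documents cannot narrow that range. As planned, the pooled figure describes those who enrolled and should not be read as prevalence in people recovering from COVID-19.

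**What to change.** 1. Record recruitment route and site for each participant. The coordinator already answers every inquiry and referral, so route can be noted at first contact.
2. Add recruitment route and current swallowing complaint to the Section 7.0 moderators. The complaint question is already on the intake form. Report both primary outcomes by complaint status and, descriptively, by route. Do not present the linked-cohort stratum as a prevalence estimate.
3. Describe the pooled result as the frequency in a volunteer and referred sample, not as prevalence in people recovering from COVID-19.

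The cost is one data field, a few extra tables and a more modest claim. Strata will be small: for 25 people and an assumed frequency of 20%, counting one observation per person, the 95% half-width is 1.96 × √(0.2 × 0.8/25) = 0.157, about 16 percentage points. The breakdown by route can therefore show gross differences only. Sample size, procedures and participant burden do not change.
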